- Patients in the control group will receive 0.25% bupivacaine HCl. 10cc will be injected bilaterally into each uterosacral ligament prior to the colpotomy incision. After entry into the posterior cul-de-sac, an additional 10cc will be injected bilaterally into the deeper uterosacral ligaments.

We plan to standardize preoperative medication, intraoperative anesthetic regimen, medication, administration in the recovery area, and discharge medication treatment (see appendix 1). Care will include key elements of a validated enhanced recovery protocol (6).

DATA COLLECTION

Demographic data including age, BMI, medical and surgical history, indication for surgery, and degree and type of pelvic organ prolapse will be collected.

Intraoperative fentanyl use will be recorded from the anesthesia record. Immediate postoperative opioid use will be retrieved from the EMR until discharge from PACU. Immediate nausea and emesis will be determined by total dose of antiemetics in PACU. Urinary retention will be determined as post void residual greater than 200 ml on catheterization or bladder scan. Patients will be offered PO opioid analgesics as first line therapy in PACU. Number and percentage of patients receiving intravenous opioids as second line therapy, thus failing PO as first line therapy in PACU will be recorded; however they will remain in the study.

Other intraoperative and immediate postoperative data will include completed procedure, surgery time, estimated blood loss, final pathology, and presence of failed voiding trial, length of stay in recovery, and numbers and reason for any unplanned admissions. Unplanned admission patients' data will be excluded and be recorded as a treatment failure.

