All patients will be discharged home with a diary to record analgesic use, VAS pain scores, and presence of nausea and emesis through 72 hours post-surgery (POD 3). Opioid use will be documented as total tablets of 5 mg oxycodone, hydromorphone 2mg, and non-opioid medication use as total tablets of acetaminophen 500 mg and/or ibuprofen 600 mg. VAS (0-10) pain scores will be logged at 6 hour intervals. Nausea and emesis will be documented as how many times patients felt nauseated, how many times they vomited, and total tablets of anti-emetic. Patients will be emailed twice a day with a link to record their documented scores. Those who prefer not to complete the surveys electronically will have the option to complete the paper questionnaire and diary. Those choosing the paper option will receive a daily phone call from study personnel blinded to study groups to remind them to complete their diary and questionnaire. Patient satisfaction for pain control will be assessed as a 0-10 scale question at the 72 hour mark and again at 7 to 10 days postop via telephone.

Allergic reaction to liposomal bupivacaine and local anesthesia toxicity will be assessed immediately on presentation to PACU, prior to discharge, and assessed by telephone and documented up to the 7 to 10th post-operative day. All doses of liposomal bupivacaine are within manufacturer labeling, and this is an FDA “on label” use of the drug (surgical site tissue infiltration). Concomitant bupivacaine HCl with liposomal bupivacaine doses are within manufacturer “on label” recommended ratio of 1:2. Intralipid 20% for local anesthetic toxicity treatment will be immediately available at all times prior to discharge. All data will be entered into HIPAA-compliant REDCap software.

SAMPLE SIZE

We plan to enroll and randomize 104 patients with the goal of obtaining complete data on at least 96 (47 per group) assuming a 10% loss to follow up. With a sample of 96, we achieve 80% power to detect a 30% difference in total opioid use at the 72 hour mark corresponding to an effect size of 0.6 at an alpha 0.05.

DATA ANALYSIS

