Statistical summary descriptives such as mean, median, standard deviation, first quartile, third quartile and range for quantitative data, and frequency and proportions for categorical data will be provided. The objectives of the study comprise the group comparisons between combination liposomal bupivacaine/bupivacaine HCl vs. bupivacaine HCl only for total opioid use in morphine equivalents, total non-opioid use, VAS pain scores, episodes of emesis, total antiemetic use, and patient satisfaction. The normality assumptions will be checked and the appropriate parametric tests such as the two independent sample t-test or non-parametric tests such as the Wilcoxon rank sum test will be used. Group associations with categorical variables will be tested using the Chi-square or Fishers' exact test. The significance level is at 0.05.

SAFETY MONITORING

All patients will be continuously monitored for local anesthetic toxicity or other reaction to liposomal bupivacaine for the entire surgical scope of care. During surgery standard ASA monitors will be in place and in recovery vital signs every 15 minutes with continuous telemetry and pulse ox, with a minimum 2:1 RN monitoring. They will remain in recovery a minimum of 4 hours post op. Continuous surveillance for medication reaction or local anesthetic toxicity including but not limited to tinnitus, perioral numbness, mental status changes, cardiac arrhythmia, respiratory compromise, rash, or hives. 20% intralipid for treatment of toxicity will be available at all times. Patients will also be discharged with specific education regarding signs and symptoms for local anesthetic toxicity and instructions to call the on call physician with mild symptoms and present to the ED if moderate or severe symptoms.

ADVERSE EVENTS

The investigator/study team will report to the Mayo IRB any UPIRTSOs and NonUPIRTSOs according to the Mayo IRB Policy and Procedures.

An adverse event is defined as an untoward or undesirable experience associated with the use of a medical product (i.e. drug, device, biologic) in a patient or research subject. All adverse events that are considered related to the direct use of liposomal bupivacaine will be defined, collected, and reported.

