APPENDIX I

DATA COLLECTION

- I. Demographic data
 - a. Age/date of birth
 - b. BMI
- II. Preoperative data
 - a. Indication for surgery
 - b. Medical history
 - c. Surgical history
- III. Operative data
 - a. Surgery performed
 - b. Operative time
 - c. Pathologic diagnosis
 - d. Total fentanyl dose in mcg during surgery
 - e. Complications during surgery; anesthetic and surgical
- IV. Immediate postoperative data (PACU until discharge)
 - a. Total opioid use in mg morphine IV equivalents
 - b. Antiemetic use as total doses IV antiemetics
 - c. VAS pain scores: cumulative in PACU until discharge
 - d. Urinary retention: determined as post void residual greater than 200 ml on catheterization or bladder scan.

V. Postoperative data to 72 hour (POD 3)

- a. Total opioid use in mg morphine IV equivalents
- b. Non-opioid medication use in total tablets of 600 mg ibuprofen and 500 mg acetaminophen
- c. VAS pain scores: mean of cumulative in PACU until discharge, day of discharge at home, 24 hours (POD 1), 48 hours (POD 2), 72 hours (POD 3). Home VAS scores will be mean of 6 hour intervals each day
- d. Times patients felt nauseated: day of discharge at home, 24 hours (POD 1), 48 hours (POD 2), 72 hours (POD 3).
- e. Episodes of emesis: day of discharge at home, 24 hours (POD 1), 48 hours (POD 2), 72 hours (POD 3).
- f. Antiemetic medication use: day of discharge at home, 24 hours (POD 1), 48 hours (POD 2), 72 hours (POD 3).
- g. Indication for admission (if applicable)
- h. Patient satisfaction with postoperative pain control (0-10; 0=unsatisfied, 10=very satisfied)
 - i. 72 hours
 - ii. 7-10 days post op

ANESTHESIA PROTOCOL

I. Preoperative:

- a. Up to 4 mg Midazolam at providers discretion on transport to OR
- b. Celecoxib 400mg PO (Gyn service order)
 - i. For patients 18-64 years old
- c. Acetaminophen 1000mg PO (Gyn service order)
- d. Decadron 4mg (Gyn service order)
- e. Gabapentin 300-600mg PO (Gyn service order)
 - i. For patients 18-59 years old, order 600mg
 - ii. For patients 60-69 years old, order 300 mg
 - iii. Do not give if >70 years old

II. Intraoperative:

- a. Study group: (OR nurse to retrieve, surgeon to inject)
 - i. Mix 20cc 0.5% bupivacaine HCl and 20 cc liposomal bupivacaine in 1:1 ratio
 - ii. Inject 10cc of mixture into each uterosacral ligament prior to colpotomy
 - iii. After entry into posterior cul-de-sac, inject additional 10cc of mixture into deeper uterosacral ligaments

- iv. Total injection = 40 ml

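### Randomised, treated patients with an unplanned admission are excluded from the data and no named analysis brings them back, so the primary 72-hour comparison is open to bias

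*Combined protocol and SAP*

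**What the plan says.** The Data Collection section lists admissions among the intraoperative and immediate postoperative items, to be recorded as "numbers and reason for any unplanned admissions". For the patients concerned, it then says their "data will be excluded and be recorded as a treatment failure". Appendix I repeats the item under postoperative data to 72 hours as "Indication for admission (if applicable)".

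The failure label is not used again. It is absent from the primary and secondary outcomes under Objectives. It is also absent from the comparisons listed under Data Analysis: "total opioid use in morphine equivalents, total non-opioid use, VAS pain scores, episodes of emesis, total antiemetic use, and patient satisfaction". The only sentence there that could apply is generic and names no variable: "Group associations with categorical variables will be tested using the Chi-square" or Fisher's exact test. No intention-to-treat set, imputation, composite or sensitivity analysis is defined.

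The sources of analgesic data also leave these patients out. For the hospital stay, "Immediate postoperative opioid use will be retrieved from the EMR until discharge from PACU". After that, "All patients will be discharged home with a diary to record analgesic use".

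A neighbouring rule goes the other way. Patients who need intravenous opioids in PACU after oral opioids fail are counted, "however they will remain in the study".

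**The concern.** Unplanned admission happens after randomisation and after the study injection. Dropping patients because of it means that the groups compared are no longer the groups randomised. If admission is related to analgesic use and acts differently in the two arms, the 72-hour comparison is biased.

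Both conditions are plausible. Poorly controlled pain, nausea and urinary retention are outcomes of this trial and can lead to an overnight stay. If the treatment works, it should change how often that happens. By calling admission a treatment failure, the plan itself links it to treatment and then removes those patients from the treatment comparison.

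The bias can go either way. If heavy users are admitted more often in the control arm, a real benefit shrinks. If they are admitted more often in the study arm, the benefit is inflated.

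**Working it through.** **Inputs from the plan.** 104 randomised 1:1 (52 per arm); 10% loss; a goal of 47 per group; effect size 0.6; a 30% difference; alpha 0.05 (two-sided assumed); 80% power; t-test or Wilcoxon test. With the control mean set to 1, a 30% difference equal to 0.6 SD gives SD = 0.30/0.6 = 0.5 and a study mean of 0.7.

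**The plan's own figure.** Two-sided t-test power has noncentrality 0.6 × √(n/2). At 48 per arm this is 2.94 and power is 82.9%. At 47 per arm it is 2.91 and 82.1%. For the Wilcoxon test (n × 0.955) power is 81.1% and 80.3%. The stated 80% is reproduced, slightly on the safe side. With all 52 per arm kept, t-test power is 86%.

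**Assumptions (not in the documents).** The control admission rate p, and the correlation ρ between admission and analgesic use. A patient is admitted when L = ρz + √(1−ρ²)e exceeds c, the (1−p) quantile of the standard normal. Here z is use standardised on the control arm, and the rule is the same in both arms. The study arm's mean L is lower by 0.6ρ, so its cut-off is c + 0.6ρ.

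**Difference among patients left in, in SD.** 0.6 − ρφ(c)/Φ(c) + ρφ(c+0.6ρ)/Φ(c+0.6ρ), multiplied by 0.5 for units of the control mean. For p = 10%, c = 1.2816:

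- ρ = 0.5: 0.6 − 0.0975 + 0.0606 = 0.563 SD, or 0.28. Excluded: 10.0% of controls, 5.7% of study patients.
- ρ = 1: 0.6 − 0.195 + 0.070 = 0.475 SD, or 0.24. Excluded: 10.0% and 3.0%.

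**Simulated t-test results, 52 per arm (40,000 trials each):**

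| Controls admitted | ρ | Difference (true 0.30) | Power |
|---|---|---|---|
| none excluded | – | 0.30 | 86% |
| 10% | 0 | 0.30 | 82% |
| 10% | 0.3 | 0.29 | 81% |
| 5% | 0.5 | 0.29 | 83% |
| 10% | 0.5 | 0.28 | 81% |
| 15% | 0.5 | 0.28 | 78% |
| 5% | 1 | 0.26 | 80% |
| 10% | 1 | 0.24 | 74% |
| 15% | 1 | 0.22 | 69% |

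If the exclusions come on top of the full 10% loss (47 per arm), the 10% case gives power of 76% at ρ = 0.5 and 69% at ρ = 1, against 82% with everyone kept.

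**Bias in either direction.** More generally, the bias in the control-minus-study difference is −(pC − pS) × m. Here pC and pS are the admission rates and m is the excess use of admitted over non-admitted patients, in SD. For 15% versus 5% and m from 0.5 to 2, this is 0.10 × 0.5 = 0.05 to 0.10 × 2 = 0.20 SD. A simulation with those rates, 47 per arm and a latent correlation of 0.5 to 0.8 turned a true 0.6 SD into 0.52 to 0.47 SD with more control admissions. With more study-arm admissions it became 0.68 to 0.73 SD.

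**False-positive rate with no true effect.** Under the same rule in both arms it stays at 5%. In the 15% versus 5% model it is about 6.5% to 11%. If 75% of admission candidates are dropped in one arm and 25% in the other (10% candidates), it is about 8% at ρ = 1 and 5–6% at ρ = 0.5. Only the extreme of all dropped in one arm and none in the other gives 15–17% (about 8% at ρ = 0.5).

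**Would comparing admission counts reveal it?** Exact enumeration of Fisher's test at 52 per arm gives power of 5% for 10% versus 6%, 14% for 10% versus 3%, and 42% for 10% versus 0%. The smallest significant imbalances are 6 versus 0 and 8 versus 1.

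**The case against.** The strongest reply is that the effect is likely to be small. These are planned outpatients. At 2–3% admitted and a correlation of 0.3 to 0.5, the difference stays at 0.29–0.30 and power at 84–85%. Patients, recovery staff and data collectors are blinded, so a common admission rule is a fair default, and under it the false-positive rate is unaffected. The surgical team is unblinded, but the documents do not say who decides on admission. The large figures need extreme assumptions. All of this stands, and it limits the size of the problem.

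The 10% loss allowance may also have been meant to cover admissions, in which case no planned power is lost. That is possible, although the plan calls it loss to follow-up. It would protect power and do nothing about bias.

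The model is also simple. It uses normal data and t-tests, and with mean 0.7 and SD 0.5 about 8% of study patients would have negative use. The Wilcoxon case with exclusions was not simulated under this model. The results should be read as orders of magnitude.

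Failures are not wholly unreported: number and reason are recorded, and the plan promises frequencies and proportions for categorical data. That could give a count by arm, but it does not restore the 72-hour data, and a test on the counts would usually miss an imbalance.

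Finally, including ward use brings prescribing into the outcome that the plan does not standardise, since the anesthesia protocol in Appendix I stops at PACU and discharge medication. This is a real cost, confined to the few patients admitted.

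**Conclusion.** The concern holds. The plan states an explicit rule, and following it removes randomised, treated patients from the primary comparison on a post-treatment event that is plausibly related to the outcome. It provides nothing to bring them back. That conclusion rests on the text and is firm.

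The size is uncertain because admission rates and reasons are not given. Under a common rule with 5–15% of controls admitted and a correlation of 0.5, a true 0.30 is seen as 0.28–0.29, with power of 78–83% instead of 86%. If only the heaviest users are admitted, it is seen as 0.22–0.26, with power of 69–80%. If admissions are rare the effect is negligible; if they are unrelated to use, there is no bias and only patients are lost. Inflation of a benefit requires more use-related exclusion in the study arm, which cannot be ruled out in advance. The plan should be corrected, but the likely size does not make this a fatal flaw.

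**What to change.** Replace the exclusion sentence in Data Collection with wording such as: *Patients with an unplanned admission remain in their randomised group; analgesic use to 72 hours is taken from the EMR while in hospital and from the diary when at home, and is included in the primary analysis.* This wording also covers a patient who goes home and is readmitted within 72 hours.

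Extend EMR opioid retrieval for these patients from PACU discharge to hospital discharge, and retrieve ibuprofen and acetaminophen use as well, because the primary outcome includes them.

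Under Objectives and Data Analysis, name unplanned admission (treatment failure) by arm, with reason, as a reported outcome compared by Fisher's exact test, and say that the test has low power.

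An optional sensitivity analysis is a Wilcoxon test giving the worst rank to pain-related admissions only. It tests a composite, so it should not replace the primary analysis.

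The cost is protocol and SAP wording plus record retrieval for a few inpatients, from a system already used for PACU data. The drawback is that inpatient and home dosing are combined on the morphine-equivalent scale, which the report should state.

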We plan to enroll women 18-85 years old who will be undergoing outpatient vaginal hysterectomy with or without concurrent prolapse repair surgeries at the Mayo Clinic Hospital in Arizona. Participants will be recruited during the preoperative visit and consented with a written form.

Exclusion criteria will include:

- Known history of hepatic disease evidenced by AST or ALT greater than normal values
- Known history of renal disease evidenced by serum Cr greater than normal values
- Known history of prolonged QT ($QT_c >$ than 500 m/s)
- Opiate tolerance noted by daily use of greater than 20 mg morphine daily oral equivalents per day for minimum one month prior to surgery
- Allergy or contraindication to amide local anesthetics, celecoxib, ketorolac, NSAIDS, acetaminophen, gabapentin, sulfa drugs, or ondansetron. Patients allergic to both oxycodone and hydromorphone

- Patients with acute GI bleed in < 6 months of study
- Adults lacking capacity to consent

MATERIALS AND METHODS

Randomization and Blinding:

Redcap software will generate a randomization list in one-to-one ratio to assign patients to either the study group (receiving both liposomal bupivacaine and bupivacaine HCl) or control group (receiving bupivacaine only). All subjects will be recruited and assigned according to their priority at admission. The pharmacist will use this randomization list and dispense the medication sequentially. Patients, care team in recovery, study team members collecting and recording data, and statisticians will be blinded to randomization assignment. The surgical team and pharmacy will be un-blinded. All patients will be documented in EMR as receiving liposomal bupivacaine to ensure the blind is maintained and to ensure that safety features in the EMR for all patients receiving liposomal bupivacaine are activated.

TREATMENT GROUPS

Patients in both groups will be given a total volume of 40ml and dose of 100 mg plain bupivacaine:

- Patients in the study group will receive a mixture of 0.5% bupivacaine HCl and liposomal bupivacaine in 1:1 ratio. 10cc of the mixture will be injected bilaterally into each uterosacral ligament prior to the colpotomy incision. After entry into the posterior cul-de-sac, an additional 10cc will be injected bilaterally into the deeper uterosacral ligaments (diagram attached as appendix 3).

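### The sample size figures disagree: 47 per group is 94, and 104 less 10% is about 94, but the plan twice says 96 (minor; the 80% power is still about met)

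*Combined protocol and SAP*

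**What the plan says.** The Sample Size section sets the number to be randomised at 104. In the same sentence it gives the number it hopes to analyse and the loss it allows for: "obtaining complete data on at least 96 (47 per group) assuming a 10% loss to follow up". The following sentence uses the same total for power: "With a sample of 96, we achieve 80% power to detect a 30% difference in total opioid use". That difference is then expressed as a standardised effect, with the significance level: "corresponding to an effect size of 0.6 at an alpha 0.05".

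Two other sections bear on this. Materials and Methods, under Randomization and Blinding, fixes equal allocation: "Redcap software will generate a randomization list in one-to-one ratio to assign patients". Data Analysis leaves the test to be chosen after a normality check: "two independent sample t-test or non-parametric tests such as the Wilcoxon rank sum test will be used". The plan does not say which of these tests the power figure assumes, whether alpha is one- or two-sided, or how the loss allowance was applied.

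**The concern.** Two figures given for the same quantity differ. With equal arms, the per-group figure and the total for complete data cannot both be right, and the total does not follow from the number randomised and the assumed loss.

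The completer target is the number against which retention will be judged and which will be reported beside the result. As written, a trial that randomises exactly 104 and loses exactly 10% would meet the per-group figure to rounding and still miss the stated minimum total. The power statement also rests on a sample that the plan's own enrolment and loss rate do not deliver. If the shortfall were large, the 80% claim would be in doubt, so the power has to be recomputed at both totals.

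**Working it through.** **Inputs.** Sample Size section: 104 randomised, 10% loss, 96 complete, 47 per group, effect size d = 0.6, alpha 0.05, power 80%. Randomization and Blinding: 1:1. Data Analysis: t-test or Wilcoxon rank sum. Assumed here: two-sided alpha, and normal data for the Wilcoxon figures.

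**1. The plan's own figure.** For 48 per group (96 in total), t-test power from the noncentral t distribution is 82.9%. The Wilcoxon figure, taken as t-test power at n × 3/π (its relative efficiency for normal data), is 81.1%. The stated 80% is therefore met with 96 and is closest to the Wilcoxon result. A one-sided test would need only about 35 to 36 per group, so it does not fit the plan's numbers.

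**2. Do the counts agree?**
- Per group to total: 2 × 47 = 94, not 96.
- Randomised to complete: 104 × 0.9 = 93.6, or 52 × 0.9 = 46.8 per arm.
- Loss implied by 96 out of 104: 1 − 96/104 = 7.7% (8 patients). By 94 out of 104: 1 − 94/104 = 9.6% (10 patients).
- Randomised needed for 96 after 10% loss: 96/0.9 = 106.7, so 107 (108 for equal arms).
- Randomised needed for 94 after 10% loss: 94/0.9 = 104.4, within one patient of 104.
- With the cruder rule of adding 10%: 94 × 1.1 = 103.4, rounded up to 104; 96 × 1.1 = 105.6, rounded up to 106.

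Neither loss rule connects 96 to 104. Both connect 94 to 104, exactly or within one patient.

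**3. Number needed for 80% power.** The t-test needs 44.6 per group. Dividing by 3/π for Wilcoxon gives 46.7, rounded up to 47. One plausible route to the plan's numbers is therefore 47 per group, 94 in total, 104 after adding 10%. This is inference; the plan does not show its calculation.

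**4. Power at each total** (d = 0.6, two-sided 0.05):

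| Complete | Per group | t-test | Wilcoxon (3/π) | Wilcoxon (simulated) | d detectable at 80% (t-test) |
|---|---|---|---|---|---|
| 94 | 47 | 82.1% | 80.3% | 80.1% to 80.3% | 0.584 |
| 96 | 48 | 82.9% | 81.1% | 81.0% | 0.578 |

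The simulation used 200,000 replicates of normal data (Monte Carlo standard error 0.1 percentage points). The range at 47 per group is with and without continuity correction. At the unrounded 46.8 per arm, power is 81.9% by t-test and 80.1% by Wilcoxon (3/π).

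**5. Size of the gap.** Two patients (2/96 = 2.1%), 82.9 − 82.1 = 0.8 points of t-test power, and a detectable effect that moves from 0.578 to 0.584, still below 0.6.

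**The case against.** The strongest reply is that nothing depends on the difference. Both totals exceed what the t-test needs, power moves by less than one point, and no analysis or conduct would change. That stands, and it is why the point is minor.

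A second reply is that the sentence can be read as two separate minimums: at least 96 in total and at least 47 in each arm, for example 47 and 49. One-to-one assignment does not guarantee equal numbers of completers. This is possible but strained, and it leaves the other contradiction in place, because a 10% loss from 104 still yields 93.6.

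A third is that readers are not left wholly in doubt, since the total is given as 96 twice. Repetition does favour 96 as the intended target, and 47 could be a slip for 48 with the loss allowance misapplied. Against that, 104, 10%, 47 per group and 80% power by Wilcoxon all fit together, which makes 96 the odd figure out. The documents do not settle it, so the sponsor has to.

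The reassurance on power is also conditional. At the lowest possible rank-test efficiency (0.864), Wilcoxon power is about 76% with 47 per group and 77% with 48. The Data Collection section excludes the data of unplanned admissions, and the plan does not say whether the 10% covers them. The link between a 30% difference and d = 0.6 cannot be checked, because no mean or standard deviation is given; it implies a standard deviation of half the control mean (0.30/0.6 = 0.5). These caveats apply to 94 and 96 alike and do not affect the arithmetic.

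**Conclusion.** The inconsistency is real and can be seen within one paragraph: the plan's enrolment, loss rate and per-group figure give about 94 with complete data, while its target and power statement say 96. The most likely explanation is that 96 should read 94, but this is not proven.

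It is minor. Taking the plan's effect size and loss rate as given, and assuming a two-sided 5% level, the 80% power claim is still about met at 94 by t-test, and by Wilcoxon if the data are close to normal. With Wilcoxon the margin over 80% is under one point, which is a reason to state the number cleanly but not a reason to doubt the design.

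**What to change.** The sponsor should confirm which total was meant and correct the Sample Size section to match.

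- **If 94 was meant (the likelier case):** replace 96 with 94 in both sentences and keep the 30% difference as the stated target. Suggested text: *We will randomise 104 women; after a 10% loss, about 94 (47 in each arm) should be evaluable. For a 30% difference in 72-hour opioid consumption, taken as a standardised effect of 0.6, and assuming a two-sided 5% level, this gives about 82% power by t-test, or about 80% by Wilcoxon rank sum if the data are near normal.*
- **If 96 was meant with 104 randomised:** change 47 to 48 and restate the assumed loss as at most 7.7%.

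Either change is a rewording of two sentences, with no effect on enrolment, conduct or analysis. Only if the sponsor wants to keep both 96 and the 10% loss would the number randomised rise, to 107 (108 for equal arms), which is three or four more patients. The power calculation does not require this.

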There are few studies evaluating liposomal bupivacaine in gynecologic surgery. Hutchins et al demonstrated that patients who received transversus abdominis plane (TAP) blocks with liposomal bupivacaine required 50% less total opioid during the first 72 hours following robotic assisted hysterectomy than patients who received bupivacaine (4). While liposomal bupivacaine is promising for management of postoperative pain, it has not yet been studied in vaginal surgery.

The aim of this study is to compare the effects of preemptive analgesia using liposomal bupivacaine mixed with bupivacaine HCl, versus bupivacaine HCl alone for uterosacral ligament injection in patients undergoing vaginal hysterectomy. We hypothesize that the group receiving a combination of liposomal bupivacaine and bupivacaine HCl will report superior postoperative pain management. Enhancement in pain control should confer a decrease in opioid and other analgesic medication requirements, which may contribute to decreased nausea, vomiting, and higher overall patient satisfaction with pain control.

OBJECTIVES

The primary aim of this study is to compare total post-surgical analgesic medication use in the first 72 hours following surgery completion (all opioids in IV morphine equivalents and total mg use of ibuprofen and/or acetaminophen combined).

Secondary outcome measures include mean PACU VAS (0-10) pain score, VAS pain score at 24, 48, and 72 hours post-surgery completion, nausea and emesis at 24, 48, and 72 hours post-surgery completion, urinary retention, and patient satisfaction with pain management at 72 hours and 7-10 days post op.

DESIGN

This is a prospective randomized, blinded, controlled clinical trial.

STUDY MEDICATION

Liposomal bupivacaine is being used per FDA indication (postsurgical analgesia) at an approved dose and route of administration (surgical site infiltration). It is also being given within the FDA labeled doses of the bupivacaine HCl given concomitantly, which recommends mg dose of bupivacaine HCl to liposomal not to exceed 1:2. Safety and efficacy of concomitant use has been prospectively studied (5). This study does not intend to pursue change to labeling or advertising. This study will be carried out in accordance with the applicable United States government regulations and Mayo Clinic research policies and procedures.

PARTICIPANTS

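### Nine or ten non-pain secondary comparisons share one unadjusted 0.05 level with no order or exploratory label, so with no treatment effect the chance of a nominally significant result favouring the study drug is about 10–22%, against 2.5% for one test

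*Combined protocol and SAP*

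**What the plan says.** OBJECTIVES sets one primary aim, analgesic use over 72 hours, and then lists secondary outcomes. Besides pain scores these are "nausea and emesis at 24, 48, and 72 hours post-surgery completion, urinary retention, and patient satisfaction with pain management at 72 hours and 7-10 days" after surgery. The introduction says that better pain control should lower analgesic requirements, "which may contribute to decreased nausea, vomiting, and higher overall patient satisfaction with pain control".

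DATA ANALYSIS presents its group comparisons as the study's objectives, in one undivided list that starts with opioid and non-opioid use and goes on to "VAS pain scores, episodes of emesis, total antiemetic use, and patient satisfaction". It then allows a t-test or Wilcoxon test for quantitative outcomes and a chi-square or Fisher's exact test for categorical ones, and ends: "The significance level is at 0.05".

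The two sections do not name the same outcomes. Nausea and urinary retention are secondary in OBJECTIVES but absent from the DATA ANALYSIS list. Total antiemetic use is in DATA ANALYSIS but is not a secondary outcome in OBJECTIVES. Neither section ranks the secondary outcomes, names a lead time point, divides alpha, makes secondary testing depend on the primary result, or calls the results exploratory.

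**The concern.** As written, every comparison is judged against the same threshold. If the 72-hour analgesic comparison showed no difference, the plan would still let one p-value below 0.05 among nine or ten non-pain outcomes be reported as a finding on nausea, emesis, retention or satisfaction. The error rate for such a result is that of the whole set, which is higher than the rate for a single test. Because the two lists differ, it is also unsettled which outcomes and time points belong to the set. What is at stake is the standing of secondary benefit claims, not the primary result.

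**Working it through.** **The plan's own figure.** The documents state no family-wise error rate. The only design calculation is in SAMPLE SIZE: "80% power to detect a 30% difference in total opioid use at the 72 hour mark corresponding to an effect size of 0.6". It matters here because it shows which sidedness the design implies.
- Normal approximation, two-sided: n = 2 × ((1.960 + 0.842) / 0.6)² = 43.6, so 44 per group.
- t-test: 44.6 per group. Divided by the Wilcoxon efficiency of 0.955: 46.7, so 47 per group, which matches the plan's per-group figure.
- One-sided: only 35 per group.

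The design is therefore reproduced with two-sided tests. I use two-sided 0.05, which gives 0.025 in the favourable direction for each test.

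**Counting the tests.**
- From OBJECTIVES: nausea 3 + emesis 3 + urinary retention 1 + satisfaction 2 = 9.
- Adding total antiemetic use from DATA ANALYSIS: 10.
- Narrowest reading, the non-pain outcomes in the DATA ANALYSIS list only: emesis 1 + antiemetic total 1 + satisfaction 2 = 4.

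Appendix I also collects nausea, emesis and antiemetic use for the day of discharge at home. I have not counted that period.

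**Formulas.** With no treatment effect and k independent tests:
- at least one result favouring the study drug: 1 − 0.975^k;
- at least one result in either direction: 1 − 0.95^k.

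For example, 1 − 0.975^9 = 1 − 0.796 = 20.4%, and 1 − 0.975^10 = 1 − 0.776 = 22.4%.

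The outcomes are surely correlated, but the documents give no correlations. I assume a common correlation ρ between normal test statistics and integrate over the shared component.

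| Tests | Direction | ρ = 0 | ρ = 0.5 | ρ = 0.7 |
|---|---|---|---|---|
| 9 | favourable | 20.4% | 13.5% | 10.1% |
| 10 | favourable | 22.4% | 14.4% | 10.7% |
| 4 | favourable | 9.6% | 7.8% | 6.5% |
| 9 | either | 37.0% | 26.9% | 20.2% |
| 10 | either | 40.1% | 28.7% | 21.3% |

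One test alone gives 2.5% (favourable) or 5% (either).

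**Check on the correlation pattern.** Ten tests simulated with higher correlation within a domain than between domains (within-domain about 0.5 to 0.85, assumed) gave 13–18% favourable and 25–34% either way. This agrees with the table.

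**Check on Fisher's test.** At 48 per group, the actual two-sided size of Fisher's exact test is about 0.7% to 2.9% for assumed event rates of 5% to 30%. If retention were analysed that way and added nothing at all, 10 tests would become 9 (10.1–20.4% favourable) and 9 would become 8 (9.5–18.3%). The chi-square test runs at about 5% to 6%, so with it the figures stand.

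**The case against.** Several points on the other side have force.

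- **Direction.** A reader might take the either-direction 20–40% as the chance of a false benefit claim, about four to eight times 0.05. The documents do not support that. A two-sided test gives only 0.025 to the favourable side, so the benefit figure is 10–22%.
- **Count.** DATA ANALYSIS gives no time points and does not name nausea or retention. That these are tested at 0.05 is the natural reading of its general test rules, not its literal text. On the four-test reading the favourable rate is 6.5–10%.
- **Hypothesis.** A reader might infer that the protocol predicts benefit on these outcomes and would treat one small p-value as confirmation. The main hypothesis concerns postoperative pain management. Nausea, vomiting and satisfaction come in a hedged downstream clause, and retention is not in it. No section says that an efficacy conclusion will rest on a single secondary result.
- **Existing hierarchy.** The outcomes are labelled secondary, power is calculated for opioid use alone, and STUDY MEDICATION disclaims any intent to change labeling. Unadjusted secondary tests are common in trials of this kind.

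All four stand, and they limit the size and consequence of the point. They do not remove it. The secondary label in OBJECTIVES has no counterpart in DATA ANALYSIS, where the same outcomes stand beside opioid use under one threshold with nothing said about how their p-values are to be read.

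**Conclusion.** The point holds as a cheap improvement to the plan. With no treatment effect, the chance of at least one nominally significant non-pain secondary result favouring the study drug is about 10–22% (13–14% at correlation 0.5), against 2.5% for one two-sided test. In either direction it is about 20–40%, against 5%. On the narrowest reading the favourable rate falls to about 6.5–10%, and Fisher's test for retention would lower the figures somewhat.

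These figures assume two-sided tests, nine or ten tests (four on the narrowest reading), normal test statistics, and a common correlation between 0 and 0.7. The correlations are my assumption.

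It would go too far to conclude that the trial's primary inference is compromised. The gap concerns how these secondary results may be interpreted, and nothing in it changes the error rate of the primary comparison.

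**What to change.** In DATA ANALYSIS, replace the closing sentence on significance with wording such as:

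*The 0.05 level (two-sided) supports a conclusion for the primary aim as defined in OBJECTIVES. The non-pain secondary outcomes (nausea, emesis, antiemetic use, urinary retention, satisfaction) are exploratory. They will be reported with group differences, 95% confidence intervals and unadjusted p-values, and no efficacy claim will be based on them alone.*

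Then use the same outcome list, with its time points, in OBJECTIVES and DATA ANALYSIS. The wording refers to the primary aim as it stands, including its non-opioid part, and leaves the handling of the VAS scores unchanged.

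If the investigators want to keep confirmatory claims on these outcomes, the alternative is Bonferroni or Holm adjustment across the set: smallest threshold 0.05 / 10 = 0.005 for ten tests, or 0.05 / 9 = 0.0056 for nine.

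The exploratory label needs a few sentences before unblinding and no extra patients, data or procedures. Its cost is that a lone secondary p-value below 0.05 can no longer be presented as a confirmed benefit.
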